8.8.3. Other Secondary Efficacy Endpoints

Analysis of other secondary efficacy endpoints PFS at 4 months, RFS at 4 months, median PFS, and median OS will be done separately for the 5 sarcoma subtypes groups. Progression-free survival is defined as the time from the first dose date to the first observation of a disease progression or death due to any cause. If a patient has not progressed or died by the data cutoff date, the PFS time will be censored at the time of the last evaluable tumor assessment.

Recurrence-free survival (RFS) is defined as the time from the first dose date to the first observation of a disease progression or recurrence/progression after surgical resection of tumor, or death due to any cause. If a patient has not progressed or died by the data cutoff date, the RFS time will be censored at the time of the last evaluable tumor assessment.

Overall survival is defined as the time from the first dose date to the date of death due to any cause. If a patient is lost to follow-up before the data cutoff date or still alive by the data cutoff date the OS time will be censored at the last contact date.

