I. Dose Escalation Phase 1 Part of Study: The study will employ the standard “cohort of three” design (2). Three patients are treated at each dose level with expansion to six patients per cohort if DLT is observed in one of the three initially-enrolled patients at each dose level. If no DLT occurs after 2 doses, escalation to the next dose level will be permitted. The maximum tolerated dose is defined as the highest safely tolerated dose, where not more than one patient experienced DLT, with the next higher dose level having at least two patients who experienced DLT. Patients in the dose escalation study may continue treatment at their designated dose levels up to eighteen 3-week cycles or until significant disease progression or unacceptable toxicity occurs. No intra-patient dose escalation will take place.

Dose of nivolumab: 3 mg/kg IV over 30 min. q 3 weeks (Day 1 of every 21-day cycle)

Dose of ABI-009:

NB: ABI-009 will start after 2nd nivolumab dose and will be administered on D8 and D15 beginning in C2.

Escalating doses IV over 30 min for 2 of every 3 weeks:

Treatment Cycle	# Pts.	Dose Level	Dose, mg/m ²
Every 3 weeks	3-6	I	56
Every 3 weeks	3-6	II	75
Every 3 weeks	3-6	III	100

Note: DLT includes any \geq Grade 3 colitis, hepatitis, or pneumonitis, any Grade 1-2 colitis, hepatitis or pneumonitis that recurs, worsens or persists with oral steroids longer than 14 days, symptoms of adrenal crisis, any Grade 4 hematologic toxicity or any \geq Grade 3 non-hematologic toxicity. If DLT develops in more than 1 patient at Dose 56 mg/m², the dose will be de-escalated to 45 mg/m² and to 30 mg/m² if DLT develops at 45 mg/m².

II. Expansion Phase 2 Part of Study: Following dose escalation, an additional 22-28 patients will receive ABI-009 at the MTD and defined doses of nivolumab to assess overall safety and potential efficacy in a greater number of patients. Patients in the expansion phase of the study may continue treatment up to 18 3-week treatment cycles or until significant disease progression or unacceptable toxicity occurs.

The study will be conducted in compliance with International Conference on Harmonisation (ICH) Good Clinical Practices (GCPs).

Surgical Resection: After three or more treatment cycles, the principal investigator may recommend surgical debulking, complete surgical removal or a biopsy. If residual disease

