End of Treatment	The date of the last dose of ABI-009 or nivolumab which ever is later for an individual patient.
End of Treatment Visit	For a patient is when safety assessments and procedures are performed after the last treatment, which must occur at least 4 weeks (\pm 7 days) after the last dose of ABI-009 or nivolumab whichever is later.
Primary Analysis	For this study will occur after all patients have either completed the study or completed 12 months of treatment. Patients who are still active at the time of the primary analysis may continue on study until disease progression or medication intolerance is observed.
Follow-up Period	The on-study time period after the End of Treatment Visit. All patients that discontinue study drug and have not withdrawn full consent to participate in the study will continue in the follow-up phase for survival and anticancer therapy. Follow up will continue approximately every 12 weeks (+/- 3 weeks), or more frequently as needed, until death, withdrawal of consent, or the study closes, whichever is the earliest. This evaluation may be made by record review and/or telephone contact.
Efficacy Analysis Dataset	All enrolled patients with measurable tumor per RECIST v1.1 at baseline who received at least two doses of ABI-009 and had a follow-up CT scan/MRI (modified treated population)
Full Analysis Set	All enrolled patients who receive at least one dose of ABI-009 (treated population).
Per-protocol Analysis Set	All enrolled patients who do not have any prospectively defined protocol violations.

Progression-free survival	The time from the first dose date to the first observation of a disease progression or death due to any cause.
Recurrence-free survival	The time from the first dose date to the first observation of disease progression or recurrence/progression after surgical resection, or death due to any cause.
Overall survival	The time from the first dose date to the date of death due to any cause.
Overall response rate	The proportion of patients who achieve a confirmed partial response or complete response per RECIST 1.1. Response rates based on a local radiologic assessment
Duration of response	The time from when criteria of response are first met until the first observation of disease progression per RECIST v1.1 or death due to any cause, whichever comes first.

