6. DESCRIPTION OF STUDY TREATMENTS (ABI-009/NIVO)

6.1. ABI-009/Nivolumab Dosage, Administration, and Schedule

For the Phase 1 part of study, patients will receive nivolumab 3 mg/kg as IV infusion over 60 min every 3 weeks, followed by escalating doses of ABI-009 56, 75, 100 mg/m² for 2 of every 3 weeks by IV infusion over 30 minutes. ABI-009 will start on Day 8 of Cycle 2. If DLT develops in more than 1 patient at Dose 56 mg/m², the dose will be de-escalated to 45 mg/m² and to 30 mg/m² if DLT develops at 45 mg/m². Patients will continue therapy until unequivocal clinical disease progression, unacceptable toxicity, or until in the opinion of the investigator the patient is no longer benefiting from therapy, or at the patient's discretion.

For the Phase 2 part of study, patients will receive nivolumab 3 mg/kg as IV infusion over 30 min every 3 weeks, followed by ABI-009 at the MTD dose for 2 of every 3 weeks by IV infusion over 30 minutes. ABI-009 will start on Day 8 of Cycle 2. Patients will continue therapy until unequivocal clinical disease progression, unacceptable toxicity, or until in the opinion of the investigator the patient is no longer benefiting from therapy, or at the patient's discretion.

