8.3. Efficacy Analysis

The Efficacy Analysis Dataset includes all enrolled patients with measurable tumor per RECIST v1.1 at baseline who receive at least two doses of ABI-009 and had a follow-up CT scan/MRI.

The disease control rate (DCR; CR+PR+SD), objective response rate (ORR; CR + PR), progression free survival (PFS), recurrence-free survival (RFS) will be assessed by an local radiologic assessment using Response Evaluation Criteria in Solid Tumors (RECIST) v1.1.

The focus of the study is to estimate the DCR in patients treated with ABI-009 and nivolumab. Patients who progress before receiving ABI-009 will be replaced, and will not be included in the statistical analysis. The number and percentage of patients achieving disease control (CR, PR or SD) will be summarized.

Analysis of other efficacy endpoints, PFS at 4 months, RFS at 4 months, median PFS, median RFS and median OS will be assessed for all subtypes together, and separately in the five sarcoma subtypes with metastatic disease and locally advanced disease. Patients may be stratified further as locally advanced or metastatic. Patients in the locally advanced tumor subgroup may be clinically indicated to receive surgery if there is sufficient tumor shrinkage, which could introduce a bias in the assessment of the PFS at 4 months, median PFS, and OS. Recurrence-free survival (RFS) defined as progression free survival + absence of disease progression or recurrence after surgical resection has been added to the secondary endpoints to obviate this bias.

PFS, RFS and OS will be summarized using Kaplan-Meier (KM) analysis. The number of patients in each category is expected to be small; therefore, PFS at 4 months, RFS at 4 months, median PFS, and median OS for these patients will be summarized by descriptive statistics.

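### PFS, RFS and OS are counted from the first dose, but patients who fail before ABI-009 starts four weeks later are left out, so the Kaplan-Meier estimates are biased upward for the regimen as started

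*Combined protocol and SAP*

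**What the plan says.** **Time origin (8.8.3).** PFS: "Progression-free survival is defined as the time from the first dose date to the first observation of a disease progression"; a death from whatever cause is also an event. RFS: "Recurrence-free survival (RFS) is defined as the time from the first dose date to the first observation of a disease progression", with recurrence after surgery and death added. OS: "Overall survival is defined as the time from the first dose date to the date of death due to any cause". The drug is not named.

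**Schedule.** The synopsis gives nivolumab at "3 mg/kg IV over 30 min. q 3 weeks (Day 1 of every 21-day cycle"). Section 6.1 says "ABI-009 will start on Day 8 of Cycle 2", and section 2.3 puts the second ABI-009 dose on Day 15 of that cycle. The synopsis puts the first response scan 6 weeks after first treatment.

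**Who is analysed.** Section 8.3 and the synopsis state: "Patients who progress before receiving ABI-009 will be replaced, and will not be included in the statistical analysis". In the list of definitions, the Full Analysis Set needs one ABI-009 dose. The Efficacy Analysis Dataset takes patients with measurable disease "who received at least two doses of ABI-009 and had a follow-up CT scan/MRI (modified treated population"). The synopsis also replaces patients who have no follow-up scan.

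**Method.** Sections 8.3 and 8.8.1 plan ordinary Kaplan-Meier. No analysis of all patients who started treatment is planned. The plan discusses bias in these endpoints only for surgery (2.2.2 and 8.3), not for the condition of reaching ABI-009.

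**The concern.** The clock starts at one event and membership of the analysis is decided at a later one. Anyone who progresses or dies in between is removed by rule, while everyone who remains is credited with that interval as event-free follow-up. This is guarantee-time (immortal-time) bias, and it can only push the curves up.

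The nivolumab lead-in is a deliberate part of the regimen: section 1.4 gives a biological rationale for giving the anti-PD-1 antibody first. A failure during the lead-in is therefore a failure of the strategy under study. Section 8.6 says the results will be used to plan later Phase 2 trials, and a reader will set the medians and PFS rates beside series counted from first dose in all treated patients. The two are not comparable.

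**Working it through.** The plan gives no planned PFS or OS value, so there is no figure of its own to reproduce.

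**1. When entry occurs, counted from Cycle 1 Day 1**
- First ABI-009 dose, Cycle 2 Day 8: 21 + 7 = 28 days (week 4).
- Second ABI-009 dose, Cycle 2 Day 15: 21 + 14 = 35 days (week 5).
- First follow-up scan: about week 6.

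**2. What is guaranteed**

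| Endpoint | One-dose set | Two-dose-plus-scan set |
|---|---|---|
| Death (OS, and the death part of PFS and RFS) | none before week 4 | none before about week 6 |
| Progression (PFS, RFS) | none recorded before week 4 | none recorded before week 4; partial from week 4 to 6 |

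The guarantee against progression is only partial after week 4. Section 2.3 allows treatment beyond RECIST progression, so such a patient can still receive the second dose and enter with the event counted. Progression on the week-6 scan is also counted.

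**3. Assumptions for size.** Exponential times with median PFS 15.3 weeks and median OS 40 weeks. These come from the single-arm ridaforolimus sarcoma trial cited in section 1.1.1 and are not planning values of this study.
- Rate for progression or death: ln2/15.3 = 0.04530 per week.
- Death rate: ln2/40 = 0.01733 per week.
- Progression rate, by subtraction: 0.02797 per week.

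**4. Upper bound: every early event detected and removed.** Reported S(t) = S(t)/S(t0), where t0 is the entry week.
- S(13) = exp(−0.04530 × 13) = 0.555.
- t0 = 4: 0.555/0.834 = 0.665.
- t0 = 5: 0.555/0.797 = 0.696.

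**5. With scans every 6 weeks.** Silent early progression is first seen at week 6 and stays in the analysis as an event. Only early deaths, and progressions found clinically before ABI-009, are lost.
- All patients started, 3 months (13 weeks, scans at 6 and 12): exp(−0.02797 × 12) × exp(−0.01733 × 13) = 0.715 × 0.798 = 0.571.
- All patients started, 4 months (17.4 weeks, same two scans): 0.715 × 0.740 = 0.529.
- Fraction retained = exp(−0.01733 × t0) × [1 − q × (1 − exp(−0.02797 × 4))]. Here q is the share of progressions before week 4 that are found before ABI-009, and 1 − exp(−0.02797 × 4) = 0.106.
- Reported PFS = the all-patient value divided by the fraction retained.

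| Lost | Set entry | Retained | 3-month PFS | 4-month PFS |
|---|---|---|---|---|
| Deaths only (q = 0) | week 4 | 0.933 | 0.571 → 0.612 | 0.529 → 0.567 |
| Deaths only (q = 0) | week 6 | 0.901 | 0.571 → 0.633 | 0.529 → 0.587 |
| Deaths and half of progressions (q = 0.5) | week 4 | 0.884 | 0.571 → 0.646 | 0.529 → 0.598 |
| Deaths and half of progressions (q = 0.5) | week 6 | 0.854 | 0.571 → 0.669 | 0.529 → 0.620 |

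The gain is about 4 to 6 points for deaths only and about 7 to 10 points with half of early progressions. Treating 15.3 weeks as time to progression, with deaths added on top, gives a similar gain: 4-month PFS goes from 0.43 to 0.46–0.48 and to 0.50–0.52.

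**6. OS.** The factor is 1/exp(−0.01733 × t0): 1.07 at week 4 and 1.11 at week 6. A median of 40 weeks would read 44 to 46. With the 90.6-week median OS of the Phase 3 ridaforolimus trial (also in 1.1.1), the factor is 1.03 to 1.05.

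**The case against.** **The first dose might mean ABI-009.** The definitions tie Study Day 1 to the investigational product, which the synopsis names as ABI-009. On that reading only 1 to 2 weeks of guaranteed time remain, from the second dose and the scan. But section 5.1 times the screening scan to study day 1 and section 5.2.4 times the same scan to C1D1, when only nivolumab is given. C1D1 is the natural reading. The ambiguity stands as a reason to name the drug.

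**The analysis set is not fixed.** Section 8.3 does not say which set the Kaplan-Meier analyses use, and the Per-protocol set has no ABI-009 condition. That is correct, but the exclusion sentence covers the statistical analysis in general, and both ABI-009-based sets are affected.

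**The study is descriptive.** All estimates are hypothesis-generating, the exclusion is stated openly, and no historical comparison is planned. With 40 to 50 patients, a 55% rate carries about ±14 to 15 points. This lowers the consequence. It does not remove a systematic shift, and the plan already added RFS to deal with a different bias in the same endpoints.

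**Early deaths should be few.** Eligibility requires ECOG 0–1 and life expectancy over 3 months, and the indications include slower diseases such as desmoid tumor. This is fair: the size depends on the hazard, and the OS effect is modest.

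**Conclusion.** The mismatch between time origin and entry condition is real, and it biases PFS, RFS and OS upward whenever anyone progresses or dies before entry. Under the stated assumptions the likely overstatement of 3- or 4-month PFS is about 4 to 10 points. The OS factor is about 1.07 to 1.11. The hazards are borrowed and the share of early progressions found clinically is assumed, so the direction is firmer than the size.

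Two stronger readings are tempting and not supported:
- *Progression-free time is guaranteed for the whole 4 to 6 weeks.* This holds for death in the two-dose-plus-scan set. For progression the firm guarantee ends at week 4, because treatment past progression is allowed and progression on the week-6 scan counts.
- *Three-month PFS would read 66.5% to 69.6% instead of 55.5%.* This needs every event before week 4 or 5 to be detected and removed, yet the first scheduled scan is at week 6. It is an upper bound.

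**What to change.** In 8.3, 8.8.3, the analysis-set definitions and the matching synopsis text:
- Name nivolumab on Cycle 1 Day 1 as the time origin.
- Add an all-treated set: every patient given a first nivolumab dose.
- Report PFS, RFS and OS from Cycle 1 Day 1 in that set, counting progression or death before ABI-009 as events. Limit the exclusion sentence so that it does not apply to these analyses.
- If an ABI-009-treated subset is also shown, start its clock at the first ABI-009 dose, include all patients who received one, and label it as conditional on reaching ABI-009.

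Delayed-entry (left-truncated) Kaplan-Meier is not a substitute. Patients enter at nearly the same scheduled time with no earlier events, so it reproduces the ordinary curve: in a simulation with median 15.3 weeks and entry at week 5, both gave 0.694 at 13 weeks, against 0.554 for all patients. If entry is set at the qualifying scan, it also loses patients who progress on that scan.

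The cost is a change of wording and slightly more analysis. The dates should already exist, since follow-up covers patients who stop treatment (2.5, 5.4) and data collection covers those not receiving protocol therapy (12.3). The reported estimates will be less favourable.

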9. MONITORING, RECORDING AND REPORTING OF ADVERSE EVENTS

9.1. Toxicities of ABI-009

ABI-009 is a formulation of rapamycin. No unexpected toxicities not already known for rapamycin (Rapamune®) or the rapamycin prodrug, temsirolimus (Torisel®), were identified in the nonclinical toxicity studies, or observed in the phase 1 studies for ABI-009.

More details on the known precautions, warnings, and AEs of rapamycin and rapalogs are found in the Rapamune® and Torisel® Package Inserts (58, 59).

9.2. Toxicities of Nivolumab

Nivolumab is an FDA approved monoclonal antibody for the treatment of advanced melanoma, non small cell lung cancer, renal cell carcinoma and bladder cancer. The toxicities of nivolumab are immune-related adverse events including immune-mediated pneumonitis, hepatitis, endocrinopathies and visual disorders. More details and known precautions, warnings and AEs are found in the product information (www.accessdata.fda.gov).

An AE is any noxious, unintended, or untoward medical occurrence that may appear or worsen in a patient during the course of a study. It may be a new intercurrent illness, a worsening concomitant illness, an injury, or any concomitant impairment of the patient's health, including laboratory test values (as specified by the criteria below), regardless of etiology. Any worsening (ie, any clinically significant adverse change in the frequency or intensity of a preexisting condition) should be considered an AE. A diagnosis or syndrome should be recorded on the AE page of the CRF rather than the individual signs or symptoms of the diagnosis or syndrome. **Note:** Disease progression and death due will not be recorded as an AE.

Abuse, withdrawal, sensitivity or toxicity to the IP should be reported as an AE. Overdose, accidental or intentional, whether or not it is associated with an AE should be reported on the appropriate CRF, see [Section 6.2.3](#) for the definition of overdose. Any sequela of an accidental or intentional overdose of the IP should be reported as an AE on the AE CRF. If the sequela of an overdose is an SAE, then the sequela must be reported on an SAE report form and on the AE CRF. The overdose resulting in the SAE should be identified as the cause of the event on the SAE report form and CRF but should not be reported as an SAE itself.

All patients will be monitored for AEs during the study. Assessments may include monitoring of any or all of the following parameters: the patient's clinical symptoms, laboratory, pathological, radiological or surgical findings, physical examination findings, or other appropriate tests and procedures.

All AEs will be recorded by the investigator from the time the patient signs informed consent until 28 days after the last dose of ABI-009 and those SAEs made known to the investigator at any time thereafter that are suspected of being related to IP. AEs and SAEs will be recorded on the AE page of the CRF and in the patient's source documents. All

SAEs must be reported to AADI Drug Safety within 24 hours of the investigator's knowledge of the event by facsimile, or other appropriate method, using the SAE Report Form, or approved equivalent form.

The investigator's clinical judgment is used to determine whether a patient is to be removed from treatment due to an AE. The investigator is responsible for ensuring that all AEs observed by the investigator or reported by the patient that occur after the first dose of IP through the EOT Visit are reported using the applicable CRF (eg, Adverse Event Summary CRF).

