A phase 1/2 investigation of safety/efficacy of nivolumab (Opdivo®) and ABI-009 (*nab*-rapamycin) in patients with advanced Ewing's sarcoma, PEComa, epithelioid sarcoma, desmoid tumor, chordoma, non-small cell lung cancer, small cell lung cancer, urethelial carcinoma, melanoma, renal cell carcinoma, squamous cell carcinoma of head and neck, hepatocellular carcinoma, classical Hodgkin's lymphoma, MSI-H/dMMR metastatic colorectal cancer, and tumors with genetic mutations sensitive to mTOR inhibitors

Study Number: SOC-1701

Study Phase: 1/2

Name of Investigational Product (IP)

ABI-009, rapamycin protein-bound nanoparticles for injectable suspension (albumin bound), *nab*-rapamycin, nanoparticle albumin-bound rapamycin

Name of FDA Approved Study Agent

Nivolumab (Opdivo®), is a programmed death receptor-1 (PD-1) blocking monoclonal antibody indicated for the treatment of patients with (1) BRAF V600 wild-type unresectable or metastatic melanoma, as a single agent, (2) BRAF V600 mutation-positive unresectable or metastatic melanoma, as a single agent. This indication is approved under accelerated approval based on progression free survival. (3) Unresectable or metastatic melanoma, in combination with ipilimumab, (4) Metastatic non-small cell lung cancer and progression on or after platinum-based chemotherapy, (5) Advanced renal cell carcinoma who have received prior anti-angiogenic therapy, (6) Classical Hodgkin lymphoma that has relapsed or progressed after autologous hematopoietic stem cell transplantation (HSCT) and post-transplantation brentuximab vedotin, (7) Recurrent or metastatic squamous cell carcinoma of the head and neck with disease progression on or after a platinum-based therapy, and (8) advanced or metastatic urothelial carcinoma who have progressed on platinum-containing chemotherapy.

Indication

Previously treated patients with advanced (metastatic or locally advanced) sarcoma, including desmoid tumor and chordoma

Objectives

Primary Objective

The primary objective of this study is to investigate the maximum tolerated dose of ABI-009, an mTOR inhibitor, when given sequentially with nivolumab in advanced UPS, LPS, OS, CS, Ewing's sarcoma.

Secondary Objectives

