In Trial 1, diarrhea or colitis occurred in 21% (57/268) of patients receiving nivolumab and 18% (18/102) of patients receiving chemotherapy. Immune-mediated colitis, defined as requiring use of corticosteroids with no clear alternate etiology, occurred in 2.2% (6/268) of patients receiving nivolumab: five patients with Grade 3 and one patient with Grade 2 colitis. The median time to onset of immune-mediated colitis from initiation of nivolumab was 2.5 months (range: 1-6 months). In three patients, colitis was diagnosed after discontinuation of nivolumab for other reasons, and Grade 2 or 3 colitis led to interruption or permanent discontinuation of nivolumab in the remaining three patients. Five of these six patients received high-dose corticosteroids (at least 40 mg prednisone equivalents) for a median duration of 1.4 months (range: 3 days-2.4 months) preceding corticosteroid taper. The sixth patient continued on low-dose corticosteroids started for another immune-mediated adverse reaction. Immune-mediated colitis improved to Grade 0 with corticosteroids in five patients, including one patient with Grade 3 colitis retreated after complete resolution (defined as improved to Grade 0 with completion of corticosteroids) without additional events of colitis. Grade 2 colitis was ongoing in one patient.

- **Immune-mediated hepatitis.** Aspartate aminotransferase (AST) or alanine aminotransferase (ALT) greater than 3 and up to 5 times upper limit of normal (ULN) or total bilirubin greater than 1.5 and up to 3 times ULN

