7.2. ABI-009 and Nivolumab Accountability, Disposal, and Compliance

For ABI-009, only completely unused study drug vials should be retained by the site until a representative from AADi or Sponsor-nominated CRO has completed an inventory. Partially used and completely used vials should be destroyed according to the site's guidelines, and their disposition should be recorded on the Investigational Drug Accountability Record Form.

For ABI-009, the Investigator, or designee, shall record the dispensing of study drug to patients and any remaining study drug after dosing in a study drug accountability record. The study drug record will be made available to AADi or authorized AADi-designated monitoring personnel for the purpose of accounting for the study drug supply. Inspections of the study drug supply for inventory purposes and assurance of proper storage will be

conducted as necessary. Any significant discrepancy will be recorded and reported to AADI or their designee and a plan for resolution will be documented.

Accurate recording of all ABI-009 administration will be made in the appropriate section of the patient's CRF and source documents. The investigator or designee is responsible for accounting for all study-specific IP either administered or in their custody during the course of the study.

For Nivolumab, the Investigator, or designee, shall record the dispensing of study drug to patients. The study drug record will be made available to AADI or authorized AADI-designated monitoring personnel for the purpose of accounting for the use of the drug.

Accurate recording of all nivolumab administration will be made in the appropriate section of the patient's CRF and source documents. The investigator or designee is responsible for accounting for all study-specific IP either administered or in their custody during the course of the study.

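### Section 9.2 gives two conflicting adverse-event windows; when nivolumab is the last drug given, collection can close 21 days after that dose, or as early as the day of it

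*Combined protocol and SAP*

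**What the plan says.** **Section 9.2.** AEs are recorded "from the time the patient signs informed consent until 28 days after the last dose of ABI-009"; after that, only SAEs suspected to be related to IP are added. The section continues: "AEs and SAEs will be recorded on the AE page of the CRF and in the patient's source documents". This is therefore a CRF window. The closing paragraph of the section then makes the investigator responsible for reporting on the CRF all AEs "that occur after the first dose of IP through the EOT Visit".

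**Other AE statements.** The Synopsis (Overview of Key Safety Assessments) and the AE row of Table 2 run from consent to 28 days after the last dose of IP. Section 9.4.2 says the same for SAEs. Section 5.1 starts AE collection at consent.

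**EOT Visit.** The definitions table places it at least 4 weeks (± 7 days) "after the last dose of ABI-009 or nivolumab whichever is later". The Synopsis (Length of Study) and Sections 2.4, 2.5 and 5.3 name either drug without saying which governs. Table 2 footnote d names ABI-009 only.

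**IP.** The Synopsis names ABI-009 as the investigational product and lists nivolumab separately as the approved study agent. The nivolumab paragraph of Section 7.2, however, says: "The investigator or designee is responsible for accounting for all study-specific IP either administered or in their custody". The definitions table makes Study Day 1 the first day of IP. Section 5.1 requires the screening scan within two weeks of Study Day 1, and Section 5.2.4 sets the same limit against Cycle 1 Day 1, when nivolumab is the only study drug given. Read together, these make nivolumab part of IP.

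**The concern.** The trial exists to describe the safety of a two-drug combination, and the characteristic nivolumab toxicities are immune-mediated and can be delayed. Section 1.3.3 itself says such reactions may occur after nivolumab is stopped. If the end of AE collection depends on ABI-009 alone, a patient whose last drug was nivolumab is observed for less time after that dose than the plan elsewhere intends.

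Once the window has closed, a non-serious event has no route into the data. A later SAE enters only if it is suspected to be related to IP, a term that may or may not cover nivolumab. Section 9.3 asks for relatedness to the IP and to protocol-required procedures, and does not name nivolumab either.

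**Working it through.** The plan states no figure on this point, so there is nothing to reproduce. The check is calendar arithmetic plus a comparison of the passages.

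**1. Calendar.** Nivolumab is given on "Day 1 of every 21-day cycle" (Synopsis). ABI-009 is given on Days 8 and 15 from Cycle 2 (Sections 1.4 and 2.3). With day(c, d) = (c − 1) × 21 + d:
- first ABI-009 dose, Cycle 2 Day 8: 21 + 8 = day 29;
- nivolumab doses before it: day 1 and 21 + 1 = day 22.

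So 28 days (days 1 to 28) and two nivolumab doses precede ABI-009.

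**2. Start of the window.** Only the last sentence of Section 9.2 starts at the first dose of IP, and only if IP means ABI-009 does that leave out days 1 to 28. The Synopsis, Table 2, Section 5.1, the first statement in Section 9.2 and Section 9.4.2 (for SAEs) all start at consent. Sections 5.2.1 to 5.2.3 also schedule AE assessment on Days 1, 8 and 15 of each cycle. The lead-in is covered, and one sentence contradicts the rest.

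**3. End of the window.** Let g be the days from the last ABI-009 dose to the last nivolumab dose. The ABI-009-anchored window closes 28 − g days after the last nivolumab dose.

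| Final sequence (example) | g | Window closes, relative to last nivolumab |
|---|---|---|
| Full last cycle: nivolumab Day 1, ABI-009 Day 15 | 1 − 15 = −14 | 42 days after |
| ABI-009 on C2D15 (day 36), nivolumab on C3D1 (day 43) | 7 | 21 days after |
| One ABI-009-free cycle, then nivolumab on C4D1 (day 64) | 28 | the same day |
| Two ABI-009-free cycles, then nivolumab on C5D1 (day 85) | 49 | 21 days before |

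A bounding case, assuming nivolumab may continue alone (the documents do not say so expressly): ABI-009 ends at C2D8 (day 29) and nivolumab runs to C18D1, day 17 × 21 + 1 = 358. Then g = 329 and the window closes on day 29 + 28 = 57.

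**4. Does the second sentence of Section 9.2 close the gap?** It ends at the EOT Visit.
- Under the definitions table, that visit falls nominally 28 days after the last nivolumab dose (21 to 35 with the tolerance). The gap is then closed, apart from the tolerance.
- Under footnote d, it falls nominally 28 − g days after that dose. This is 21 days (14 to 28) in the one-week case and 0 days (−7 to +7) with one ABI-009-free cycle. The gap is not closed.

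**5. Can nivolumab be the last drug?** The definitions table presupposes that it can, since it takes whichever drug is later. Table 5 holds ABI-009 for the rest of a cycle after Grade 3 or higher hematologic toxicity, and Section 6.2.2.1 stops ABI-009 permanently for potential hepatotoxicity; neither mentions nivolumab. Against long runs without ABI-009, Section 6.2.1 says a delay after a missed dose should not exceed 14 days and requires Medical Monitor approval to restart after 21 days.

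**6. Patients who never receive ABI-009.** An end date counted from the last ABI-009 dose does not exist for them. The definitions-table anchor supplies one.

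**The case against.** A reader might infer from Section 9.2 that CRF reporting runs from the first ABI-009 dose to 28 days after the last, so that events in the four-week lead-in are lost. The text does not support this. No sentence has both of those limits: the one that starts at IP ends at the EOT Visit, and the one that ends at 28 days starts at consent and also records on the CRF. It is also not settled that IP excludes nivolumab.

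A reader might also infer that AE rates will be biased low, citing the nivolumab trial in Section 1.3.3. There, 6 patients had immune-mediated colitis, and "In three patients, colitis was diagnosed after discontinuation of nivolumab for other reasons"; so were 2 of 6 pneumonitis and 1 of 3 hepatitis cases. Those counts do not show loss. The documents do not say how long after the last dose the diagnoses came, and any made beyond 28 days would be missed by a corrected 28-day window too. Patients who never receive ABI-009 are outside the Full Analysis Set used for safety, so their missing end date cannot distort those tables.

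The gap at the end is also conditional. After a completed cycle the ABI-009 anchor is the later one and gives 42 days after nivolumab. A shortfall needs nivolumab as the last drug and a site that follows footnote d over the definitions table. While nivolumab dosing continues, the scheduled visits still prompt AE assessment.

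All of this stands, and it limits the point to the end of the window. It does not remove it: footnote d belongs to the schedule that sites work from, it agrees with the explicit ABI-009 wording in Section 9.2, and the IP wording in the Synopsis, the Table 2 AE row and Section 9.4.2 reads the same way on the synopsis meaning.

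**Conclusion.** Section 9.2 contains two incompatible AE windows, IP is used in two senses, and the EOT Visit has two anchors. The lead-in is an internal contradiction only.

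The substantive fault is that when nivolumab is the last drug given, the ABI-009-anchored window closes 21 days after that dose in the one-week case, and on the day of the dose if one ABI-009-free cycle precedes it. This assumes 21-day cycles on schedule, a last ABI-009 dose on Day 15, and use of footnote d. AE counts can then be incomplete. How often this would happen, and how many events it would cost, cannot be estimated from the documents. No statistical figure in the plan changes, and no effect on the MTD is shown.

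**What to change.** Define IP once, saying whether it includes nivolumab. Then state one AE and SAE window: from informed consent to 28 days after the last dose of ABI-009 or nivolumab, whichever is later. Use it in the Synopsis (Overview of Key Safety Assessments), the AE row of Table 2, both statements in Section 9.2, and Section 9.4.2. Bring Table 2 footnote d into line with the definitions table.

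The visit tolerance allows an EOT Visit at day 21, so the text should say that the 28-day limit, not the visit date, ends collection. State the relatedness question in Section 9.3, and the provision for later SAEs, in terms of the defined IP or of both drugs by name. The single window also gives an end date to patients who never receive ABI-009.

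The cost is wording and a few more AEs recorded.
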